3.4 Malaria Rapid Diagnostic Test

Malaria infection status will be assessed on all enrolled children using a rapid diagnostic test (RDT) at baseline.

[figure not shown]
Supplies

- Mobile data collection device & accessories
- RDT test packet
- Alcohol swabs
- Gloves
- Lancet
- Buffer
- Timer

Conduct the Malaria RDT

1. Check the expiry date on the test packet. If the expiry date has passed, choose another packet that has not yet expired.
2. Put on the gloves. Use new gloves for each patient.
3. Open the packet and remove:
 - a. The test
 - b. The capillary tube
 - c. The desiccant sachet

[figure not shown]
4. Write the patient's name and study ID number on the test
5. Open the alcohol swab. Grasp the 4th finger on the patient's left hand. Clean the finger with the alcohol swab. Allow the finger to dry before pricking.
6. Open the lancet. Prick patient's finger to get a drop of blood.
7. Discard the lancet into an appropriate sharps receptacle immediately after pricking the finger.
8. Use the capillary tube to collect the drop of blood.
9. Use the capillary tube to put the drop of blood into the square hole on the test marked "A."
10. Discard the capillary tube into an appropriate sharps receptacle
11. Add 6 drops of buffer into the round hole marked "B."
12. Wait 15 minutes after adding buffer
13. Read test results. Do NOT read the test sooner than 15 minutes after adding the buffer.
You may get false results
14. How to read the test results:
 - a. POSITIVE: a line near letter "C" and a line near letter "T" means the patient is positive for malaria.

[figure not shown]
- i. The test is positive even if the line near "T" is faint

- b. NEGATIVE: a line near letter "C" and NO LINE near letter "T" means the patient does NOT have malaria

- c. INVALID RESULT: NO LINE near letter "C" and one or no line near letter "T" means the test is INVALID

- i. Repeat the test using a new RDT and a new lancet if no control line appears

15. Dispose of gloves, alcohol swab, desiccant sachet, and packaging

16. Record the test result in the mobile application.

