2. STUDY DESIGN

This randomized controlled trial is designed to determine the effect of administration of azithromycin compared to amoxicillin as part of the treatment of uncomplicated SAM in children aged 6-59 months on weight gain and nutritional recovery. We will randomize children presenting to Taimaka-run nutritional programs at health centers in Gombe State, Nigeria to a single dose of oral azithromycin or a short course of oral amoxicillin upon admission into the program. Apart from the administration of antibiotics, all children will receive standard outpatient treatment for uncomplicated SAM as specified in the guidelines of the government of Nigeria, which includes therapeutic feeding with RUTF. Enrolled children will be followed weekly at each routine clinic follow-up visit up until nutritional recovery. All enrolled children will return for a final study visit at 8 weeks following enrollment. Anthropometric and vital status data will be collected at each follow-up visit. Weight gain and nutritional recovery over the 8-week study period will be compared by arm as a primary outcome and at 12 weeks as a secondary outcome.

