- **MUAC.** Mid-upper arm circumference will be measured at all follow-up time points.
- **WAZ.** Weight will be measured at all follow-up time points and weight-for-age z-scores will be calculated.
- **WHZ.** Weight and height, assessed at all follow-up time points, will be used to calculate weight-for-height z-scores.
- **Malaria.** Rapid diagnostic tests for malaria will be conducted at baseline and week 8 to determine malaria infection status.

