9. STATISTICAL METHODS

9.1 Sample Size and Power

Specific Aim 1 We assume that inclusion of 600 children (300 randomized to each arm) will provide 80% power to detect a 15% increase in weight gain (g/kg/day) in children receiving azithromycin compared to children receiving amoxicillin at an alpha of 0.05. Assumptions for this calculation were based on the pattern of weight gain reported in a trial of routine amoxicillin for uncomplicated SAM in Burkina Faso comparing children receiving azithromycin to amoxicillin over time.¹¹ We assumed an average weight gain of 2.6 g/kg/day over 8 weeks in the amoxicillin arm, with a standard deviation of 1.7 g/kg/day, and loss to follow-up of 10%. A 16% increase corresponds to a mean difference in weight gain of 0.4 g/kg/day, or an average weight gain of 3.0 g/kg/day in the azithromycin arm.

This calculation was performed in Stata using the following command:

```
power twomeans 2.6, sd(1.7) alpha(0.05) power(0.8) n(540)
```

Specific Aim 2. Inclusion of 600 children (300 randomized to each arm) will provide 80% power to detect a 12 percentage point difference in the proportion of children achieving nutritional recovery in the azithromycin arm compared to the amoxicillin arm. Assumptions for this calculation were based on nutritional recovery reported in the amoxicillin arm of a trial of routine amoxicillin compared to azithromycin for uncomplicated SAM in Burkina Faso.¹¹ We assumed that 36% of children in the oral amoxicillin arm would achieve nutritional recovery and a loss to follow-up of 10%.

This calculation was performed in Stata using the following command:

```
power twoproportions 0.36, alpha(0.05) power(0.8) n(540)
```

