9.2 Statistical Analysis

Baseline characteristics. Characteristics of the study population collected at baseline will be summarized using frequencies and percentages for categorical variables and means and standard deviations or medians and inter-quartile ranges for continuous variables. Baseline characteristics will be compared by treatment arm using Fisher's exact test for categorical variables and t-tests or Wilcoxon rank-sum tests for continuous variables.

Specific Aim 1. The primary analysis will compare weight gain velocity (g/kg/day) between groups over the 8-week follow-up period. We will estimate mean differences and 95% confidence intervals for the difference using a linear regression model with an indicator for study group.

$$E[Y | X = x] = \beta_0 + \beta_1 X + e$$

Where:

- **Y = weight gain velocity from enrollment to 8 weeks**
- X = binary indicator for treatment group ($X=1$ for azithromycin, $X=0$ for a short course of oral amoxicillin)

- β_1 = difference in weight gain velocity between the azithromycin group compared to a short course of oral amoxicillin group
- $e \sim N(0, \sigma^2)$

Sensitivity analyses will include similar linear models to assess period-specific weight gain by group from week 0-1, 1-2, 2-4, and 4-8.

Specific Aim 2. The primary analysis will compare nutritional recovery by 8 weeks from baseline by arm. We will use log-binomial regression for this analysis to estimate the risk ratio. We will use the following model:

$$\log[P(Y = 1|X_1 = x_1)] = \beta_0 + \beta_1 X_1 + e$$

Where:

- **Y = binary indicator for nutritional recovery by 8 weeks ($Y=1$ for recovered, $Y=0$ for not recovered)**
- X = binary indicator for treatment arm ($X=1$ for azithromycin, $X=0$ for a short course of oral amoxicillin)
- e^{β_1} = relative risk of nutritional recovery in azithromycin arm compared to a short course of oral amoxicillin arm
- $e \sim N(0, \sigma^2)$

If the log-binomial model fails to converge, we will use a modified Poisson model with robust standard errors as an alternative.

Secondary outcomes.

Time to event outcomes (time to recovery and time to mortality) will be assessed visually using Kaplan-Meier curves and compared by arm using the log-rank test.

Binary outcomes will be analyzed using modified Poisson regression for rare outcomes (e.g. mortality) or log-binomial regression for common outcomes (e.g. malaria), using models similar to the one described above for Specific Aim 2.

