Anthropometric assessments will be analyzed using linear models as described for Specific Aim 1, with correction for baseline values. For anthropometric assessments, z-scores will be calculated based on the 2006 WHO Child Growth Standards. Anthropometric z-scores will be analyzed as continuous variables and secondary analyses will explore categorization.

All analyses will be intention-to-treat. A significance level of 0.05 for inference and 95% confidence intervals will be reported for all effect estimates. All analyses will be conducted using R (R Foundation for Statistical Computing, Vienna, Austria). For all models, model diagnostics will be conducted to assess appropriate fit.

Missing data.

If $\leq 10\%$ of enrolled children is missing outcome data, complete case analyses will be conducted. If $> 10\%$ of enrolled children are missing outcome data, inverse probability weighting will be used to weight complete cases by the inverse of an estimate of the probability of an outcome being observed as a sensitivity analysis. Weights will be constructed with the following

baseline characteristics chosen as factors likely to predict follow-up: SES, distance from health center, WHZ, and MUAC.

REFERENCES

2. Page AL, de Rekeneire N, Sayadi S, et al. Infections in children admitted with complicated severe acute malnutrition in Niger. *PLoS One*. 2013;8(7):e68699. doi:10.1371/journal.pone.0068699

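### Section 3.4 omits the week-8 malaria test that sections 2.5 and 2.6 require, and the malaria model leaves out the baseline test result

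*Combined protocol and SAP*

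**What the plan says.** **Timing of the rapid diagnostic test (RDT).** Section 3.4, which holds the supplies list and the step-by-step test instructions, says: "Malaria infection status will be assessed on all enrolled children using a rapid diagnostic test (RDT) at baseline". The malaria outcome in section 2.5 says: "Rapid diagnostic tests for malaria will be conducted at baseline and week 8 to determine malaria infection status". The participant timeline in section 2.6 lists a malaria RDT under week 8. Section 2 brings every child back at that time: "All enrolled children will return for a final study visit at 8 weeks following enrollment".

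**Analysis.** Section 9.2 assigns malaria to "log-binomial regression for common outcomes (e.g. malaria), using models similar to the one described above for Specific Aim 2". The only explanatory variable in the Aim 2 model is the arm: "X = binary indicator for treatment arm ($X=1$ for azithromycin, $X=0$ for a short course of oral amoxicillin". If the log-binomial fit for Aim 2 fails to converge, modified Poisson regression with robust standard errors replaces it. Growth outcomes are handled differently: "Anthropometric assessments will be analyzed using linear models as described for Specific Aim 1, with correction for baseline values". Section 9.2 does not say at which visit malaria is compared between arms.

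**The concern.** There are two loose ends on one secondary outcome.

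The first is that the section describing how to do the test gives a narrower schedule than the section defining the outcome. Each neighbouring procedure states its follow-up times: anthropometry (3.2), oedema (3.5), vital status (3.6) and clinical examination (3.7). Read against that pattern, section 3.4 looks like a baseline-only procedure. An RDT result describes one moment, so a test missed at week 8 cannot be recovered, and week 8 is the only RDT planned after randomisation.

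The second is that every child has a baseline RDT, yet the stated model does not use it. If infection status at enrolment predicts status eight weeks later, the arm comparison is less precise than data already in hand would allow. The plan already makes this kind of correction for anthropometry, and no reason is given for treating malaria differently.

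**Working it through.** **1. Schedule, side by side.**
- Section 2.5: baseline and week 8.
- Section 2.6: week 8 listed.
- Section 2: all children attend at week 8.
- Section 3.4: baseline named, week 8 not named, and no word such as 'only'.

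Three places support a week-8 test in every child, and one omits it.

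**2. The plan's own figure for the model that malaria borrows.** Section 9.1 says: "Inclusion of 600 children (300 randomized to each arm) will provide 80% power to detect a 12 percentage point difference". It assumes 36% recovery on amoxicillin and 10% loss, hence 600 × 0.90 = 540 analysed, or 270 per arm. With p1 = 0.36, p2 = 0.48, pooled p = 0.42 and two-sided alpha 0.05 (sidedness is not stated):

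z = [0.12 × √270 − 1.96 × √(2 × 0.42 × 0.58)] / √(0.36 × 0.64 + 0.48 × 0.52) = (1.972 − 1.368) / 0.693 = 0.871

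This gives power of 80.8%, which agrees with the stated 80%. No rate or power is stated for malaria, so no stated figure is in dispute.

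**3. Precision for week-8 malaria.** Inputs not in the documents, taken as assumptions: week-8 positivity p of 10% to 40%, and correlation ρ between baseline and week-8 status of 0.1 to 0.5. With n = 270 per arm:
- Unadjusted standard error of the risk difference: √(2p(1−p)/n).
- With the baseline RDT in the model: multiply by √(1−ρ²).
- Example at p = 0.30: √(2 × 0.30 × 0.70 / 270) = 0.0394, and 1.96 × 0.0394 = 7.7 percentage points. At ρ = 0.3 the factor is √0.91 = 0.954, giving 7.4 points.

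| ρ | Cut in standard error | Equivalent gain in sample size, 1/(1−ρ²) − 1 | 95% CI half-width at p = 30% |
|---|---|---|---|
| none used | – | – | 7.7 points |
| 0.1 | 0.5% | 1% | 7.7 |
| 0.2 | 2.0% | 4% | 7.6 |
| 0.3 | 4.6% | 10% | 7.4 |
| 0.5 | 13.4% | 33% | 6.7 |

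The unadjusted half-widths at p = 10%, 20% and 40% are 5.1, 6.7 and 8.3 points. The proportional cuts are the same at each.

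**4. What these correlations mean.** If positivity is 30% at both visits, week-8 positivity is 0.30 + 0.70ρ in baseline positives and 0.30 − 0.30ρ in baseline negatives. That is 37% against 27% at ρ = 0.1, 51% against 21% at ρ = 0.3, and 65% against 15% at ρ = 0.5.

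**5. Check on the risk-ratio scale.** Modified Poisson models with and without the baseline RDT were fitted to simulated trials (540 children, no arm effect, 600 trials per setting, positivity 20%, 30% and 40%, equal at both visits). The standard error of the log risk ratio fell by about 0% at ρ = 0.1, 3% to 5% at ρ = 0.3, and 12% to 14% at ρ = 0.5. This agrees with the formula.

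**The case against.** The best reply is that this is an omitted phrase and an optional covariate. Section 3.4 does not exclude week 8, two other sections schedule the test, and every child attends. Most of section 3.4 is a bench procedure, and the study forms in Appendix 2, whose content is not in the available text, may already show the test at week 8. The primary Aim 1 model is also arm-only, so an arm-only malaria model is consistent with the rest of the plan. Malaria is one of many secondary outcomes and is not powered.

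Most of this stands, and it rules out several stronger readings that a reader might infer:
- **That week-8 malaria will go uncollected.** The documents read together provide for it. The exposure is limited to staff who follow section 3.4 alone.
- **That the unadjusted comparison is biased.** With 1:1 randomisation it is valid, and its confidence interval already allows for chance imbalance at baseline.
- **That the baseline test serves no purpose.** Section 9.2 summarises and compares baseline characteristics, and the RDT can appear there.
- **That mixing persisting and new positives is a defect.** The outcome in section 2.5 is infection status, not new infection.

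What the reply does not remove is the mismatch between sections 3.4 and 2.5, the unstated analysis time point, and the unused baseline value that could be added at almost no cost.

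**Conclusion.** The point holds as a minor one. Section 3.4 conflicts with sections 2.5 and 2.6 on when the RDT is done and should be brought into line. The malaria model is valid but forgoes a precision gain from data already collected: about 0.5% to 5% of the standard error if ρ is 0.1 to 0.3, and about 13% if ρ is 0.5. These figures rest on 270 analysed children per arm, which follows from the plan, and on assumed positivity and correlation, which the documents do not give. The gain is small unless baseline and week-8 status are strongly related. At 30% positivity the half-width falls by at most about one percentage point over the range examined. The documents do not show that baseline RDT is the strongest predictor available.

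**What to change.** - **Section 3.4:** name both baseline and week 8 as test times, to match sections 2.5 and 2.6.
- **Section 9.2:** state that the week-8 RDT result is the malaria outcome compared between arms.
- **Section 9.2:** prespecify the baseline RDT result as a covariate in that model, and say that the modified Poisson fallback given for Aim 2 applies here too if the log-binomial fit does not converge.

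The cost is one phrase in the procedure, one sentence on the time point and one model term. Both tests are already planned, so no visit, sample or procedure is added. The covariate should be fixed before treatment codes are linked to outcomes, so that it is not a post hoc choice. An extra analysis of week-8 positivity among baseline-negative children answers a different question. It is optional and not part of this change.

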3.5 Assess for bilateral pitting oedema

Assessing for oedema will be done at enrollment to ensure eligibility and will also be assess at each weekly visits

1. While child is sitting, grasp both feet in your hands. Apply firm thumb pressure to the tops of both feet for three full seconds (count 101, 102, 103). Remove the thumbs.
2. If the depression from your thumbs remains on both feet, then the patient has bilateral pitting oedema. It may be easier to feel this depression than to see it.
3. If tops of feet are edematous, repeat the process on the shins and hands.
4. If the shins / hands are edematous, observe for oedema around the eyes.

Oedema is nutritionally significant if it is present on both feet. However, bilateral pitting also be caused by medical conditions such as nephritic syndrome. Medical causes should be first ruled out before the diagnosis of nutritional Oedema is made.

Grades of oedema

Grade of oedema	Observation
Absent	Absent, no oedema
Grade +	Mild: both feet / ankles
Grade ++	Moderate: both feet + lower legs
Grade +++	Severe: generalized oedema including both feet, legs, hands, arms and face/head

Grade +

Grade ++

Grade +++

Only children with grade + and grade ++ will be eligible to participate in the study.

3.6 Vital Status

Vital status will be recorded at all follow-up visits up to 12 weeks after inclusion. Information about whether the child is alive, has died, or has moved will be recorded. Date of death and location of move will be recorded.

3.7 Clinical examination

Outcomes of clinical examinations will be collected at enrollment, weekly follow-up visits, and at week 8. Clinical examinations will be conducted according to the standard of care in the management of SAM. Recorded outcomes include diagnoses made and treatments given/recommended.

4. STUDY MEDICATION

Children enrolled in the study will be offered weight-based, directly observed, oral suspension azithromycin plus placebo or a short course of oral amoxicillin. We will monitor adverse events following treatment as described in Section 5.

4.1 Study Medication Description

The azithromycin used in the trial will be suspension Azithromycin (Everdestiny) made by Everdestiny Pharmaceutical Limited.

The oral amoxicillin routinely used at each OTP for treatment of uncomplicated severe acute malnutrition, which is suspension Amoxicillin (Emzor) by Emzor pharmaceuticals limited, will be used for this trial.

The placebo used in this trial to mask participants in the azithromycin arm will be made by a local pharmacy.

All medications and placebo used in the trial will be placed in generic bottles at the local pharmacy to blind participants to the trial arm. The study nurse and investigators will be unblinded to the bottles

4.2 Dosage Information

Azithromycin will be administered as a single dose, in oral suspension form for children. Dosing will follow the WHO recommendations for treatment of active trachoma: Single dose of 20mg/kg in children (up to the maximum adult dose of 1g).

The placebo given to individuals in the azithromycin arm will be instructed to administer the placebo at a volume equivalent to the amoxicillin dose.

Individuals who are allergic to macrolides/azalides will not be treated.

Oral amoxicillin will be administered for 5 days. The first dose will be administered by the health agent, who will teach the caregiver how to administer the medication at home. The remaining doses will be administered by the caregiver.

Amoxicillin will be administered at a dose of 40mg/kg twice per day for 5 days.

4.3 Medication Procurement

Azithromycin, placebo, and amoxicillin will be purchased locally in Nigeria by the study team. Enrolled participants will incur no costs associated with the study medication.

4.4 Medication Quality Control

Study medication will be stored at each site prior to use. The study team and site staff will regularly check and record the study medication expiration dates. The expiration dates on the medication containers will be strictly monitored and all expired study medicine will be discarded appropriately. The study coordinator will work with each health facility to ensure that they have appropriate stock of all study medications.

5. ADVERSE EVENTS

5.1 Adverse Event Monitoring and Reporting

Parents or guardians of enrolled children will be instructed to report any adverse events experienced within the 7 days following the enrollment visit, by phone or in person. At all follow-up visits, study staff will inquire about the child's experience of adverse events, including if the child had any of the following symptoms:

- Fever
- Diarrhea
- Vomiting
- Abdominal pain
- Skin rash
- Constipation

The study team will assess whether the parent or guardian sought care for the child since the last visit and if so, what the reason was for the health care visit and if the child was hospitalized.

Serious adverse events will be defined as death, hospitalization, or any other life-threatening situation. Serious adverse events will be reported to the Medical Monitor within 24 hours.

The health agent conducting the follow-up visit will email the Taimaka investigators if a serious adverse event is diagnosed, the Taimaka investigators will immediately email the Medical Monitor and the UCSF study team. The Medical Monitor will make a determination as to whether the event could be reasonably considered to be related to the study drug and will report the results of this determination to the study investigators, who will report to the UCSF IRB and the DSMC as needed. Information on all adverse events, serious and non-serious, will be recorded on data collection forms through the mobile application.

See Appendix 5 for more information on SAE reporting.

5.2 Inpatient Hospitalization Transfer Information

OTP staff will screen children for conditions requiring referral to hospital care. Referrals will occur at multiple points, including:

1. Enrollment
2. All follow up visits

Pathways to the ITP (Inpatient Treatment Program):

SAM patients are referred to the ITP using a referral card, and their expenses are paid by the Taimaka Project.

Referrals during Triage

Triage refers to the process of identifying patients in need of urgent treatment. Triage will occur in the OTP waiting area and should be conducted as soon as possible after caregivers and children arrive. During triage, OTP staff complete two main steps:

1. Identify children with danger signs and immediately refer them to hospital care.
2. Check children for signs of measles and immediately isolate suspected cases.

Emergency Health Check:

On arrival at the OTP waiting area, each child will be immediately assessed for danger signs, which are health conditions that require urgent hospital care. Danger signs include:

1. Unconscious
2. Lethargy, not alert
3. Unable to move/extreme weakness
4. Convulsions/fits/seizures
5. Difficulty breathing

For children enrolled in the trial who exhibit any of these signs, a triage assistant will assign the child a registration number and fill out the referral form and admissions form with basic information such as the name of child and caregiver, admissions number, and phone number, and accompany the child and caretaker to the ITP.

Referrals during Anthropometric Assessment

In some cases, conditions identified during anthropometric assessment should prompt a referral to the ITP. These fall into three main categories:

1. Any child with grade 3 (++) oedema should receive a urinalysis test strip to measure protein. If the result is less than 2, they should be referred to the ITP.
2. Any child <6 months who has SAM should be referred to the ITP.
3. At weekly visits, children showing certain signs of non-response should be referred to the ITP.

Oedema:

Any child with grade 3 (++) oedema should be referred to the ITP. Additionally, OTP staff should request a urinalysis test for children with grade 1 (+) or grade 2 (++) oedema. This test will be carried out by the lab assistant. The results of this test will be used to identify non-nutritional causes of oedema, such as kidney problems. A protein result of >2 indicates that the child may have non-nutrition oedema. Children with non-nutritional oedema should be advised to visit a hospital to check for other health problems. These steps are outlined in the table below.

Additionally, because nutritional oedema begins in the feet and moves upward, caregivers should also be asked where the oedema began. If it did not begin in the feet, advise the caregiver to visit a hospital.

SAM patients should be referred to the ITP in the event of:

Criterion	Time after admission into OTP
Severe complications (defined in next lecture)	At any visit
Failure to gain any weight (non-edematous children)	21 days
Weight loss since admission to program (non-edematous children)	14 days
Failure to start to lose edema	14 days

Edema still present	21 days
Weight loss of 5% of body weight (non-edematous children)	At any visit
Failure of appetite test	At any visit
Failure to start to gain weight satisfactorily after loss of edema (kwashiorkor) or from day 14 (marasmus) onwards. Satisfactory is determined as 'at least 5 g/kg of body weight per day.'	At any visit
Failure to gain weight (rule out RUTF sharing, selling, other noncompliance, etc.) (non-oedematous children)	Any 14 day interval
Weight loss for two successive visits	At any visit
No MUAC gain for two consecutive weeks	At any visit

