2.5 Outcomes

Primary Outcome

Weight gain over 8 weeks (Specific Aim 1). Weight will be measured at all follow-up time points and weight gain will be defined as grams per kilogram per day (g/kg/day).

Secondary Outcomes

Nutritional recovery by 8 weeks (Specific Aim 2). Nutritional recovery will be defined as a child having WHZ \geq -2 on two consecutive visits and no acute complication or edema for the past 7

[figure not shown]
days AND / OR MUAC of $\geq 125\text{mm}$ on 2 consecutive visits and no acute complication or edema for the past 7 days. The criteria chosen to define the recovery will be the same one we used to admit the child into the program as defined in the national guidelines:

Criteria of admission	Criteria of discharge
MUAC < 11.5cm	MUAC > 12.5cm (for 2 consecutive weeks) Sustained weight gain Clinically well
Bilateral oedema	MUAC > 12.5cm No oedema for 2 consecutive visits Clinically well
WHZ < -3 SD	MUAC > 12.5cm AND WHZ >-2 for 2 consecutive visits Clinically well

- **Weight gain over 12 weeks.** Weight will be measured at all follow-up time points and at 12 weeks after admission to the program. Weight gain will be defined as grams per kilogram per day (g/kg/day).
- **Time to recovery.** Time from enrollment to nutritional recovery (defined above) will be calculated in days by subtracting the date of enrollment from the date of nutritional recovery.
- **Nonresponse at 8 weeks.** Nonresponse will be documented if a child does not meet the criteria for nutritional recovery at 8 weeks.
- **Transfer to inpatient care.** The occurrence, date, and reason for transfer from outpatient to inpatient treatment will be recorded.
- **Mortality by 8 weeks.** Vital status will be assessed at all follow-up time points and mortality will be defined as death during the study period. Date of death will be recorded.
- **Mortality by 12 weeks.** Vital status will be assessed at all follow-up time points and mortality will be defined as death during the study period. Date of death will be recorded.
- **Clinical signs of infection.** At all follow-up time points, clinical signs of infection will be recorded, including care-giver reported experience of fever, diarrhea, vomiting, and respiratory infection/cough and clinical diagnoses made at by site personnel
- **Adverse events.** Adverse events will be reported at all follow-up time points
- **HAZ.** Height or length will be measured monthly and height-for-age z-scores will be calculated.

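### Section 5.2 gives two conflicting referral rules for grade 3 oedema, and its 5 g/kg/day weight-gain row is not reconciled with the planned mean gains of 2.6 and 3.0 g/kg/day

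*Combined protocol and SAP*

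**What the plan says.** **Grade 3 oedema.** Section 5.2, Referrals during Anthropometric Assessment, asks for a urine protein strip in a child with grade 3 oedema and refers the child to the inpatient programme if the result is below 2. Under the Oedema subheading, the same section refers any child with grade 3, without that condition. It asks for urinalysis in grades 1 and 2 and treats a result above 2 as a sign of a non-nutritional cause. Both places give grade 3 the two-plus symbol, which the second also gives to grade 2. Section 3.5 uses three plus signs for the severe grade.

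**Weight-gain row.** The referral table in Section 5.2 includes "Failure to start to gain weight satisfactorily after loss of edema (kwashiorkor) or from day 14 (marasmus) onwards", with satisfactory set at "at least 5 g/kg of body weight per day" and the timing column allowing the check at any visit. Other rows concern children with no gain at all, for example "Failure to gain any weight (non-edematous children") at 21 days.

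**Planning figures.** Section 9.1: "We assumed an average weight gain of 2.6 g/kg/day over 8 weeks in the amoxicillin arm, with a standard deviation of 1.7 g/kg/day", and "an average weight gain of 3.0 g/kg/day in the azithromycin arm".

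**Where referrals are counted.** Transfer to inpatient care is a secondary outcome in Section 2.5: "The occurrence, date, and reason for transfer from outpatient to inpatient treatment will be recorded". Section 5.1 states: "Serious adverse events will be defined as death, hospitalization, or any other life-threatening situation".

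**The concern.** On grade 3 oedema, staff cannot follow both rules when the urine result is 2 or more: one paragraph withholds the referral and the other requires it. The shared symbol adds a risk of misreading a grade.

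On weight gain, a rate has no meaning without an interval. This row gives none: it could be since the last visit, over 14 days, since admission or since oedema loss. It also does not say whether the test is repeated. The idea of failing to start suggests that one success is enough, whereas the open-ended period and the any-visit timing suggest continued checking. Neighbouring rows do state an interval or a number of consecutive visits.

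The choice matters because the threshold lies well above both planned means. Under one reading, referrals triggered by weight gain could dominate a secondary outcome and the serious adverse event count. Under another they might be far fewer. Centres that read the row differently would record different transfer rates for similar children.

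**Working it through.** **1. The oedema rules side by side.**

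| Situation | Section 5.2, Anthropometric Assessment | Section 5.2, Oedema |
|---|---|---|
| Grade 3, urine result below 2 | refer | refer |
| Grade 3, urine result 2 or more | not referred under this rule | refer |
| Urine result exactly 2 | outside the below-2 rule | outside the above-2 rule |
| Symbol for grade 3 | two plus signs | two plus signs (same as grade 2) |

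Section 3.5 gives the severe grade three plus signs. No arithmetic is needed: the second row of the table is a direct conflict.

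**2. The plan's own figure.** Inputs from Section 9.1: SD 1.7, 270 per arm after 10% loss, 80% power, alpha 0.05 (taken as two-sided). Detectable difference = (1.960 + 0.842) × 1.7 × √(2/270) = 0.41 g/kg/day, or 0.41/2.6 = 15.8%. The plan reproduces; at the rounded difference of 0.4 the power is 78.1%. The planning means and SD can therefore be taken as stated.

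**3. Distance of the threshold from the planned means.**
- Amoxicillin: (5 − 2.6)/1.7 = 1.41 SD.
- Azithromycin: (5 − 3.0)/1.7 = 1.18 SD.

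**4. Share below 5 on the 8-week average.**
- Under normality: Φ(1.41) = 92.1% and Φ(1.18) = 88.0%.
- For any distribution (one-sided Chebyshev bound): at least 1 − 2.89/(2.89 + 2.4²) = 66.6% and 1 − 2.89/(2.89 + 2.0²) = 58.1%.

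The row starts at day 14 or after oedema loss, so the 8-week average is only a guide. As an extreme, put all the gain into days 14 to 56. The means become 2.6 × 56/42 = 3.47 and 3.0 × 56/42 = 4.00. With SD 1.7 to 2.27 (1.7 × 56/42), normality gives 75–82% and 67–72% below 5. The distribution-free minimum then falls to 31–45% and 16–26%, so a majority is no longer guaranteed.

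**5. Share meeting the row, by reading, using weekly intervals.** The documents give no within-child weekly SD, so w is an assumption. Weekly gain = child mean + independent weekly noise with SD w. The between-child variance is set to 1.7² − w²/8, so that the 8-week SD stays at 1.7. This caps w at √(8 × 2.89) = 4.81. Gain is flat over time and every child is followed to day 56.

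| Assumed weekly SD | Between-child SD | Never reaches 5 in the six weekly intervals from day 14: mean 2.6 | Same: mean 3.0 |
|---|---|---|---|
| 1 | 1.66 | 74% | 66% |
| 2 | 1.55 | 48% | 40% |
| 3 | 1.33 | 28% | 22% |
| 4 | 0.94 | 16% | 13% |
| 4.8 | 0.10 | 11% | 8% |

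- *Repeated check*, where any single weekly interval ending at day 14 or later counts if below 5: 97–100% over the same range.
- *Met once*: 8–74%, as tabulated. With two front-loaded growth profiles and weekly SD 2 to 4, the range is 20–67%.

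**6. Measurement resolution.** Section 3.2 records weight to 0.1 kg. For a child of 6 kg (assumed), one scale step over a week is 100/(6 × 7) = 2.4 g/kg/day, about half the threshold. The choice of interval therefore affects who meets the row.

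**The case against.** The strongest reply on weight gain is that nothing here is strictly contradictory. The planning gains are 8-week averages based on another trial. The row concerns gain after day 14 or after oedema loss, at visits. Weekly follow-up runs only until recovery and Section 9.1 assumes 36% recovery in the amoxicillin arm, so recovered children leave the weekly checks while the calculation keeps everyone to day 56. That stands, and the percentages are indicative only.

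The row's place beside the no-gain rows might seem to rule out a repeated check, which would make those rows nearly redundant. The table overlaps with itself on any reading, so this settles little.

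Appendix 4, the standard medical protocol, is listed without its content and may define the interval. Section 5.2 mentions a table of oedema steps that does not appear in the text available for this review; it may deal with a result of exactly 2 and with the symbol. Neither possibility removes the conflict between the two paragraphs on grade 3.

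Differences between centres are possible rather than shown: staff are trained regularly (Section 2.2), and the OTP manager supervises adherence (Section 3.1). Grade III is excluded at enrolment, so the oedema conflict reaches only enrolled children who worsen later.

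Harm to the safety data is also limited. The transfer reason is recorded, and Section 5.1 provides that "The Medical Monitor will make a determination as to whether the event could be reasonably considered to be related to the study drug". However, no analysis in Section 9.2 uses the reason.

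**Conclusion.** The grade 3 oedema conflict is wrong as written and rests on no assumption. The weight-gain row is a lesser point: a threshold 1.41 and 1.18 SD above the planned means, with no interval and no repeat rule. As a repeated check it would indicatively catch a large majority (92% and 88% on the 8-week average under normality; at least 67% and 58% on that average for any distribution). If met once, the share is about 8–74%. That range is conditional on an assumed weekly SD of 4.8 down to 1, on flat gain and on complete follow-up.

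A reader might infer more than this supports:
- *That most children will be transferred, or that a particular number of serious adverse events will follow.* The documents give no rate after day 14 and no uptake of referral, so no count can be derived.
- *That the met-once reading would surely refer only a small minority.* That holds only if weekly rates vary widely within a child, which the documents do not show.
- *That the trial is biased.* The row applies equally to both arms and outcome assessors are masked. The gap between 92% and 88% merely restates the assumed treatment effect. No effect on the primary comparison is shown.

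**What to change.** 1. Reconcile the two Section 5.2 paragraphs on grade 3 oedema with each other and with the grading in Section 3.5: when referral applies, which symbol denotes the grade, and how a urine result of exactly 2 is handled.
2. Reconcile the 5 g/kg/day row with the planning gains in Section 9.1. State the interval over which gain is measured and whether the check is repeated or met once. If Appendix 4 already says so, a cross-reference is enough.
3. In Section 9.2, keep transfer for any cause as the secondary outcome. Add a breakdown by arm, from the recorded reason, of transfers and hospitalization events for complications or danger signs versus those triggered by weight gain.

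The clinical content of items 1 and 2 is for the sponsor's clinicians to decide. The cost is a short protocol amendment, a sentence in the analysis section and one table. The transfer reason is already collected, so no new data are needed and the sample size does not change.
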